Our secondary objective is to estimate the effect of ImCT compared to psychoeducation on 1) level of depression, mania and anxiety and 2) general functioning and level of hopelessness (secondary outcome variables), 3) number of relapses into mania or depression and 4) changes in imagery characteristics. We hypothesise that (2a) symptoms of depression, mania and anxiety decrease and (2b) general functioning increase and level of hopelessness decrease (secondary outcome variables) more strongly in BD patients receiving ImCT than psychoeducation at T2, T3 and T4. Additionally, the effects of both treatments separately are also compared to baseline period preceding both treatments. We also hypothesise that 3) number of relapses into mania or depression after the end of ImCT are lower in the ImCT condition during the follow up period (T4) than in the psychoeducation condition. Finally, we hypothesises that 4) imagery characteristics will change more and problematic imagery decreases in the BD patients receiving ImCT at T2, T3 and T4, compared to baseline.

Note that, our primary outcome variable, mood variability, is measured in two ways. First, at baseline (T0), pre-intervention (T1), T2, T3 and T4. Second, mood variability is measured daily, during the four weeks baseline, during the intervention, and during the follow-up period (in total 16 weeks post intervention), in both the ImCT and psychoeducation conditions. Further note that the secondary outcome variables (2a), level of depression, mania and anxiety, are measured weekly throughout the duration of the study in both conditions and the secondary outcome variables (2b) general functioning and level of hopelessness and (4) changes in imagery are only measured at T0, T1, T2, T3 and T4. All measures are administered using an online secure server called Research Manager.

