3. STUDY DESIGN

The present research proposal concerns a randomised feasibility trial, comparing ImCT intervention to psychoeducation. In addition to the between group design, the study also uses a within-group design, where ImCT and psychoeducation is preceded by a four-week baseline condition. Note that during this baseline period and throughout the study, all patients will maintain their regular appointments with their psychiatrist or specialised nurse practitioner, who will prescribe, monitor and adjust mood stabilising medication conform guidelines. The within-group design allows participants baselines to act as their individual control periods with no intervention (Barlow, Nock, & Hersen, 2009; Bonsall, Wallace-Hadrill, Geddes, Goodwin, & Holmes, 2012; Holmes et al., 2016). The study will take place within a specialised centre for bipolar disorders within a large psychiatric hospital (GGzE). All participants start after 4 weeks of baseline with either ImCT or psychoeducation treatment. The duration of the study for participants will be 32 weeks for participants in the ImCT condition and 26 weeks for participants in the psycho-education condition. The difference in duration between the conditions is due to treatment length, that is, 12 weeks weekly 1-hour sessions for ImCT and 6 weeks weekly 2-hour sessions for the psychoeducation treatment. Note that all participants will have had 12 hours face-to-face contact in both conditions.

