4.2 Inclusion criteria

In order to be eligible to participate in this study, a subject must meet all of the following criteria:

- Aged 18-68
- Sufficient Dutch language ability to permit the assessment to be completed.
- Diagnosis of BD (I or II or unspecified) according to DSM-5 (clinicians assessment).
- Willing to complete daily and weekly monitoring throughout the duration of the study.
- Successful completion of the daily monitoring in the 4 weeks active run-in phase.
- Willing to be randomised to either ImCT or psychoeducation condition
- Able to attending 12 consecutive weekly sessions ImCT or 6 weekly two hours sessions psychoeducation/TAU.

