6. METHODS

6.1 Study parameters/endpoints

6.1.1 Main study parameter/endpoint

To assess the primary endpoint of this study (1), decrease of mood variability, mood variability is measured using the Affect Lability Score Short Version (ALS-18) (Oliver & Simons, 2004) at baseline (T0), pre- intervention (T1) and post intervention (T2), and at follow-up measurements at 8 (T3) and 16 weeks (T4) after treatment discontinuation in both the ImCT and psychoeducation conditions. The ALS-18 is a self-report scale measuring lability in affect and consists of 18 items. Ratings are made on a 4-point scale with a maximum score of 72. Scores range from A= very characteristic of me (4 points), to D= very uncharacteristic of me (1 point).

In addition we monitor changes in mood variability using the National Institute of Mental Health Life Chart Methodology (NIMH-LCM) Prospective Self-Rating (Denicoff et al., 2000). Participants rate their mood (both mania and depression) on a 9-point Likert scale, ranging from -4 (severe depression, admission required due to severe dysfunction) to 0 (stable mood) to +4 (severe mania, admission required due to severe dysfunction). Daily measurements are calculated during a 4-week baseline prior to start of either ImCT or psychoeducation, during the intervention and until follow up at 16 weeks. This method is advised given that traditional self-report mood ratings over a single time point are scarcely representative of mood variability in bipolar disorder.

6.1.2 Secondary study parameters/endpoints (if applicable):

The following parameters are used for the following secondary objectives:

To assess (2a) level of depression, mania and anxiety and (2b) general functioning and hopelessness (3) number of relapses into mania or depression decline/increase, we administer the following measures:

- Level of depression, using the Quick Inventory of Depressive Symptoms (QIDS-SR) (Rush et al., 2003). The QIDS-SR is a 16-item self-report rating scale in which the nine DSM 5 symptoms of major depression are incorporated. Answers are rated on a four-point Likert scale (0-3). The QIDS-SR is administered weekly throughout the duration of the study.

- Level of mania, using the Altman Self-Rating Mania Scale (ASRM-NL) (Altman, Hedekker, & Peterson, 1997). The ASRM-NL is a 5 item self-report instrument to measure severity of mania symptoms. This is administered weekly throughout the duration of the study.

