8. STATISTICAL ANALYSIS

First, descriptive analyses will be used to establish mean scores, standard deviations and to identify outliers. Missing data from our primary outcome variable, will be listwise deleted. In our other outcome variables, data will only be included if pre- and post-measures are completed.

Second, the data will be checked with respect to violation of assumptions (such as error independency, non-normal distributions) for variance-based models.

Primary outcome variable: mood variability:

To assess if there is a stronger decrease in mood variability in the ImCT intervention condition as compared to the psychoeducation condition, multivariate repeated measures analyses are applied. Dependent variables are the scores on the ALS-18 (baseline, T0; pre-treatment, T1; post-treatment, T2; 8-weeks follow-up, T3; 16-weeks follow-up, T4) with treatment condition (ImCT, psychoeducation) as between subjects variable.

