In addition, to assess reductions in mood variability during the interventions (ImCT, psychoeducation) compared to mood variability during the baseline period, daily mood measures with the National Institute of Mental Health Life Chart Methodology (NIMH-LCM) Prospective Self-Rating of mood (both mania and depression) are assessed, using a case series design, where participants baseline ratings can act as their own control (Arntz, Sofi, & van Breukelen, 2013). Changes in mood variability are investigated using sequence analysis with R-software (package TraMineR version 1.8-10); (Gabadinho, Ritschard, Muller, & Studer, 2011) on the daily scores. Sequences consist of a series of subsequent states (daily scores) and similarities between sequences are calculated with the Optimal Matching technique (OM). Sequences will be defined as day scores from 28 days prior to starting the interventions, until 112 days after the end of interventions. Rather homogenous groups of trajectories (clusters) will be derived from the distance matrix that result from the OM technique. To this end, cluster analysis will be applied. Shannon entropy of transversal state of the scores on each day will be calculated and plotted (Gabadinho et al., 2011). Entropy is a measure of diversity of states (a measure of mood variability) within sequences and varies between zero (all sequences in the same state) to 1 (maximum diversity). To explore the relationship between diversity in states (mood variability) and background characteristics, this longitudinal entropy will be regressed on co-variates (gender, medication). Also, sequences of scores at the start of treatment will be compared to subsequences during treatment and during the follow-up period to explore change over time.

Secondary outcome variables: depression, anxiety, mania, general functioning and coping, hopelessness, number of relapses into mania or depression, and changes in imagery:

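### Listwise deletion, applied as written to the daily mood ratings, removes a patient for one missed day in 182 or 224; section 8 needs a separate rule for missed days.

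*Combined protocol and SAP*

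**What the plan says.** - Section 2 states that "our primary outcome variable, mood variability, is measured in two ways": the ALS-18 at T0 to T4, and daily ratings through baseline, intervention and follow-up.
- Section 8 gives two missing-data rules. For the primary outcome: "Missing data from our primary outcome variable, will be listwise deleted". For the rest: "In our other outcome variables, data will only be included if pre- and post-measures are completed". Neither mentions a single missed day, and the listwise rule names no unit (day, window or patient).
- Under the primary-outcome heading, section 8 then treats the daily ratings as state sequences: "Sequences consist of a series of subsequent states (daily scores". Their span is fixed: "Sequences will be defined as day scores from 28 days prior to starting the interventions, until 112 days after the end of interventions". They feed Optimal Matching, clustering and Shannon entropy. No rule for gaps is given there.
- Section 3 gives the study length as "32 weeks for participants in the ImCT condition and 26 weeks for participants in the psycho-education condition".
- Section 4.2 makes eligibility depend on "Successful completion of the daily monitoring in the 4 weeks active run-in phase", with no threshold for success. Sections 6.3.2 and 9.2 place randomisation after those four weeks.
- The last paragraph of section 8 makes intention-to-treat the central analysis, with completers as a supplement.

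**The concern.** Patients enter a rating every day for 26 or 32 weeks, so gaps are to be expected. Section 1 says that retention on daily monitoring is one of the things the trial is meant to estimate, so near-perfect completion cannot be assumed. A rule that may suit five ALS-18 questionnaires becomes very severe over about 200 daily entries.

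At stake is who remains in the daily analysis. Patients without a gap are the most adherent ones and may differ in mood stability. At equal daily compliance the longer ImCT sequence loses more patients. Dropping randomised patients for one missed entry also cannot be squared with intention-to-treat. If analysts set the rule aside once data are in, they must choose a treatment of gaps after seeing the results. One available choice, counting a missed day as a further state, would distort entropy.

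**Working it through.** **Inputs from the documents.** Baseline 28 days, treatment 6 or 12 weeks, follow-up 112 days, 48 patients per arm (section 4.4), nine mood scores (section 6.1.1). **Assumed, because not stated:** the share of days missed, how far misses cluster within patients, and the illustrative mood pattern.

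**1. Sequence length, against the plan's own durations.**
- Psychoeducation: 28 + 42 + 112 = 182 days = 26 weeks.
- ImCT: 28 + 84 + 112 = 224 days = 32 weeks.

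Both agree with section 3. The plan gives no figure for daily completeness to reproduce.

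**2. Independent misses.** With a share q of days missed, P(no gap) = (1 − q)^L.

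| q | Psychoeducation, L = 182 | ImCT, L = 224 | Expected complete of 96 |
|---|---|---|---|
| 1% | 0.161 × 48 = 7.7 | 0.105 × 48 = 5.1 | 12.8 |
| 2% | 0.025 × 48 = 1.2 | 0.011 × 48 = 0.5 | 1.7 |
| 5% | 0.0 | 0.0 | 0.0 |

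**3. Clustered misses.** Let each patient's daily completion probability follow a beta distribution with mean μ and intra-person correlation ρ. Then a = μ(1/ρ − 1), b = (1 − μ)(1/ρ − 1), and P(no gap) = B(a + L, b) / B(a, b). With μ = 0.95:

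| ρ | a, b | Psychoeducation | ImCT | Expected complete of 96 |
|---|---|---|---|---|
| 0.1 | 8.55, 0.45 | 0.244 × 48 = 11.7 | 0.223 × 48 = 10.7 | 22.4 |
| 0.3 | 2.217, 0.117 | 0.583 × 48 = 28.0 | 0.569 × 48 = 27.3 | 55.3 |

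Even the milder case loses 96 − 55.3 = 40.7 patients, or 42%. ImCT keeps fewer than psychoeducation in every row with an appreciable number left.

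**4. Why a missed day should not be a state.** If a share m of days is missed and coded as a tenth state, entropy becomes H(m) = h(m) + (1 − m)H, where h(m) = −m ln m − (1 − m) ln(1 − m). Baseline and later windows must use the same divisor, ln 10 = 2.303. For an assumed patient spending 70/15/10/5% of days in four scores, H = 0.914:
- no missed days: 0.914 / 2.303 = 0.40
- 10% missed: (0.325 + 0.823) / 2.303 = 0.50 (+26%)
- 20% missed: (0.500 + 0.731) / 2.303 = 0.53 (+35%)

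Mood is unchanged throughout. Baseline is selected for adherence and later windows are not, so this coding would tend to hide a real fall in variability. It does not always act upward: for highly labile mood the sign reverses at about 30% missed, and for moderate variability between 40% and 50%.

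**The case against.** **The listwise sentence may mean the ALS-18 only.** The ALS-18 analysis comes first after it. But nothing in the sentence limits it, and section 2 places the daily ratings inside the primary outcome. If it is limited, no rule for missed days remains. Section 8 needs amending on either reading.

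**The loss may be smaller.** This is largely right. Section 4.4 counts 70 points, baseline plus at least six weeks of treatment. Over those windows alone (70 and 112 days), independent misses at 1% leave 23.8 + 15.6 = 39 of 96, and at 2% leave 11.7 + 5.0 = 17. If every randomised patient also had a gap-free baseline, the clustered case at a mean of 5% would leave about 44 (20.8 + 22.8) to 77 (37.9 + 38.8) of 96. However, section 8 defines the sequences over the full span, and section 4.2 does not guarantee a gap-free baseline. Section 4.4 also says four cases suffice for a case series. That speaks to minimum numbers, not to selection on adherence.

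**Stronger readings that the documents do not support.** A reader might infer that:
- the daily analysis would certainly be emptied. That depends on an unstated completion rate and on misses being spread evenly over patients.
- the plan codes missed days as a state and so inflates entropy. It nowhere says so.
- every day-by-day entropy fails when a patient has a gap. The entropy across patients on a given day can be computed from whoever rated that day.
- eligibility ensures a complete baseline. Successful completion has no threshold, so baseline is selected for adherence and no more.
- the comparison of arms on entropy is biased. Section 8 specifies none: it regresses entropy on gender and medication, and the powered between-arm measure is the ALS-18.

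**Conclusion.** The point holds in limited form. As written, the listwise rule covers a primary-outcome measure for which it is unsuitable: one gap in 182 or 224 days removes the patient. Under the assumed rates the analysis keeps about 13 of 96 patients (1% missed, independent), about 2 (2%, independent), or about 22 to 55 (mean 5%, clustered with correlation 0.1 to 0.3). The firm conclusions are that the loss could be large, would be selective on adherence, would be greater in ImCT at equal compliance, and conflicts with intention-to-treat. The exact size is unknown. The entropy figures only show why one tempting coding should be ruled out in advance; they do not describe what the plan does. The sample size rests on the ALS-18, so this should be corrected before analysis but does not undermine the powered between-arm comparison.

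**What to change.** Amend section 8 as follows:

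1. State that listwise deletion does not apply to the daily ratings.
2. Compute each patient's entropy in each window (baseline, treatment, follow-up) from rated days only, and do not count a missed day as a mood state.
3. Include a patient-window when a stated minimum share of its days is rated, and repeat the analysis at one other threshold (75% and 50% would serve as an illustration).
4. State how gaps enter the Optimal Matching distances and the clustering. The rated-days rule for entropy does not settle this.
5. Report the share of days rated by arm and window beside the result. This also supplies the daily-monitoring information that section 1 seeks.

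The cost is a few sentences and one sensitivity run. Two downsides should be acknowledged: sparse patient-windows drop out, and using rated days only does not correct for days missed because of a mood episode.

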Where possible multivariate analyses are used to analyse differences between groups, and repeated-measures ANOVA to analyse difference within groups. These will be used to minimise the correlations and dependencies between variables. In order to allow for reliable multivariate analysis, assumptions of sphericity are tested. Multivariate analyses between groups (ImCT, psychoeducation treatment) and repeated-measures ANOVA within groups (T0, T1, T2, T3, T4) are used to determine an omnibus effect. If differences are significant, post hoc analyses (mostly independent T-test) will be used to determine individual differences between groups and between points in time. Bonferoni corrections are used to correct for multiple testing.

Intention-to-treat analyses will constitute the central analyses and completers analyses will be done as supplementary analyses.

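### The daily mood-variability analysis merges entropy across patients with entropy within a patient, and does not specify how change from each patient's own baseline will be measured or tested

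*Combined protocol and SAP*

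**What the plan says.** Section 2 states that mood variability, the primary outcome, is measured in two ways: by the ALS-18 at T0-T4 and by daily ratings. It also says that each treatment will be compared with the baseline period before it. Section 3 gives the reason: "The within-group design allows participants baselines to act as their individual control periods with no intervention".

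For the daily ratings, Section 8 states the aim as "to assess reductions in mood variability during the interventions (ImCT, psychoeducation) compared to mood variability during the baseline period". It then specifies:

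- **Sequence definition:** "Sequences will be defined as day scores from 28 days prior to starting the interventions, until 112 days after the end of interventions".
- **Plot:** "Shannon entropy of transversal state of the scores on each day will be calculated and plotted".
- **Interpretation:** "Entropy is a measure of diversity of states (a measure of mood variability) within sequences and varies between zero (all sequences in the same state".
- **Regression:** "this longitudinal entropy will be regressed on co-variates (gender, medication", with the stated purpose of exploring background characteristics.
- **Change over time:** "sequences of scores at the start of treatment will be compared to subsequences during treatment and during the follow-up period", described as exploratory.

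Section 4.4 contrasts 28 baseline points with at least 42 treatment points, 70 in all, and mentions calculating and testing difference scores. Elsewhere in Section 8, "repeated-measures ANOVA within groups (T0, T1, T2, T3, T4) are used to determine an omnibus effect".

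**The concern.** There are two linked problems.

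First, one quantity is given incompatible meanings. An entropy calculated per day across patients has one value per day and belongs to no patient. The text then describes it as diversity within a sequence, which is a patient-level property, but sets its zero point where all sequences share a state, which is an across-patient property. Next it is called longitudinal and regressed on gender and medication, which needs one value per patient. A reader who takes the plotted curve as evidence of stabilisation could be misled in either direction. The curve falls if patients' average levels converge, and it moves little if each patient becomes steadier around a different level.

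Second, the own-baseline question has no stated index, window, change score or test. These would be chosen after the data are seen, for what Section 2 calls the second measure of the primary outcome.

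**Working it through.** **Inputs from the documents.** Nine states, -4 to +4 (Section 6.1.1). Baseline 28 days (Section 4.4). Treatment 12 weeks = 84 days for ImCT and 6 weeks = 42 days for psychoeducation (Section 3). Follow-up 112 days (Section 8). 45 per group and two-sided 0.05, both set for the ALS-18 (Section 4.4).

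**Assumptions.** The documents give no daily SD or autocorrelation. I used daily SD 0.5, 1 and 1.5; lag-1 correlation 0, 0.5, 0.8 and 0.95; SD of patients' mean levels 0.7 and 1.0; and log-SD 0.3 for differences between patients in daily SD. That makes 3 x 4 x 2 = 24 settings.

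**1. The plan's own figure.** 28 + 42 = 70 reproduces. It is baseline plus treatment for psychoeducation only; for ImCT the sum is 28 + 84 = 112. Whole sequences are 28 + 42 + 112 = 182 days (26 weeks) and 28 + 84 + 112 = 224 days (32 weeks), in line with Section 3.

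**2. The two entropies.**
- Transversal, day t: H_T(t) = -Σ p_k(t) ln p_k(t) / ln 9, where p_k(t) is the share of patients in state k on day t.
- Longitudinal, patient i: H_L(i) = -Σ q_k(i) ln q_k(i) / ln 9, where q_k(i) is the share of patient i's days in state k.

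**3. Limiting cases.** Nine patients, each constant at a different level: H_T = 1 and H_L = 0. Nine patients cycling through all nine states in step for 28 days: H_T = 0. In H_L one state then occurs on 4 days and eight states on 3 days each, so H_L = [(4/28) ln(28/4) + 8(3/28) ln(28/3)] / ln 9 = 0.998. The two measures can sit at opposite ends of the scale on the same data.

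**4. Intermediate cases.** Simulated AR(1) daily series, rounded and clipped to -4..+4, 28 days, 20,000 patients per setting:

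| True change | Longitudinal | Transversal |
|---|---|---|
| Every patient's daily SD halves | falls 31-49% | falls 5-22% |
| Spread of patients' levels halves, within-person variability unchanged | changes by at most 2% | falls 3-25% |

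For example, with daily SD 1, correlation 0.5 and level SD 1.0, halving the within-person SD lowers longitudinal entropy from 0.598 by 39% and transversal entropy from 0.827 by 13%.

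**5. Why window length has to be fixed.** Longitudinal entropy rises with the number of days even when nothing changes. For an assumed peaked distribution over the nine states, mean H_L at 28, 42 and 84 days is 0.703, 0.725 and 0.745 with independent days. It is 0.531, 0.588 and 0.668 if a state carries over to the next day with probability 0.7. Against 28 baseline days the spurious rise is therefore about 0.02-0.06 over 42 days and 0.04-0.14 over 84 days. With equal 28-day windows the spurious change is at most 0.02 SD of change.

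**6. Whether another part of the plan supplies the test.**
- The phase comparison in Section 8 starts from the beginning of treatment (possibly loose wording for baseline) and names no index or test.
- Section 4.4 mentions difference scores but defines none, and its lengths are unequal (28 against at least 42, with 84 in ImCT).
- The within-group ANOVA in Section 8 covers T0-T4, not the daily ratings.
- Optimal matching and clustering group trajectories; they do not test change.

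**7. Sensitivity of a paired test.** With 45 per arm, two-sided 0.05 and 80% power, the normal approximation gives (1.96 + 0.84)/√45 = 0.42. The t-based solution is 0.43 SD of change.

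**The case against.** The strongest reply is that the merging is a drafting slip. Each entropy appears where it would fit: the transversal one is plotted by day, and the longitudinal one is regressed on patient characteristics. Only the zero point and the word linking the two sentences blur them, and the plan never says that the plot is the evidence of within-person change. This is fair as to intent. The text still presents them as one measure of mood variability, so someone following it could read the wrong one.

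Three stronger readings are tempting, and the documents do not support them.

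- **That the regression is faulty because it has no phase or arm term.** Its stated purpose is the relation with background characteristics, and for that it needs neither. It simply does not address change.
- **That the plan cannot answer its baseline question.** Sequences begin 28 days before treatment, a comparison with treatment and follow-up subsequences is planned, and Section 4.4 states the contrast. The plan does not specify how the question will be answered, which is a weaker criticism.
- **That the arms will be biased because treatment lasts 84 against 42 days.** The plan does not say that entropy will be computed over full phases. On the whole sequences it does define (182 against 224 days), the spurious arm difference under the assumed settings is only 0-0.19 SD.

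It can also be said that the daily analysis is exploratory and secondary to the ALS-18 in a feasibility trial. Parts of Section 8 do use exploratory language. But the stated aim is to assess reductions, Section 2 makes the ratings a second measure of the primary outcome, and Section 4.4 claims adequate power for this design.

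**Conclusion.** The point holds and should be fixed before the daily data are analysed. The inconsistency in the entropy definition and the missing change score, window and test follow from the text alone. The percentages rest on the assumed daily SD, autocorrelation and spread of levels, so they indicate the order of size only. The finding that the two entropies respond to different things does not depend on those values, as the limiting cases show. The ALS-18 comparison and its sample size are not touched.

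**What to change.** Change Section 8 as follows.

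- Name and define transversal and longitudinal entropy separately. Keep the transversal plot, the regression and the clustering as descriptive.
- Use a within-person index for the own-baseline question. The plan's longitudinal entropy suffices. Within-person SD or RMSSD (root mean square of successive differences) is an option that respects distances on the scale: over 28 days, alternating -4/+4 and alternating 0/+1 both give entropy ln 2/ln 9 = 0.315, while their SDs are 4.07 and 0.51.
- Compute the index in equal 28-day windows. For treatment, take either the last 28 days or the average of successive 28-day windows. The average uses more days and stays closer to the stated aim. In psychoeducation 42/28 = 1.5, so its windows must overlap (days 1-28 and 15-42); in ImCT 84/28 = 3 fit exactly.
- Define change as the treatment (or follow-up) value minus the 28-day baseline value. Name one main contrast and test it with a paired test within each arm.
- Describe any between-arm contrast as supportive to the ALS-18.

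The cost is SAP wording, since the ratings are already scheduled. The downside is that some rated days may not enter the index. With three 28-day windows (baseline, last 28 treatment days, last 28 follow-up days), 3 x 28 = 84 days are used, leaving 182 - 84 = 98 unused in psychoeducation and 224 - 84 = 140 in ImCT. If only the last 28 treatment days are used, the question becomes late-treatment variability, and the plan should say so.

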Next to the ALS-18 as primary measure, we also use daily mood variability scores, using the NIMH-LCM, for the within subjects-design. Here the assessment are compared between baseline (4 weeks is 28 measuring points) conditions and both treatment conditions (at least 6 weeks is 42 measuring points). As we use 70 measuring points in total only a small number of cases suffices to calculate and test differences scores. That is, for such a case series analyses, a sample size of 4 or more is sufficient (Barlow et al., 2009). Moreover, Bulte and Onghena (Bulte & Onghena, 2009) stress that to achieve a large effect size ($d = 1.5$) and a study powered at 80%, a study would need a minimum of 4 participants with a minimum of 20 measurements per person. Our study meets those requirements.

Finally, it is important to note that this is a feasibility study following an audit on ImCT (Hales et al., 2018), and a pilot study on ImCT (Holmes et al., 2016), and precedes and plans to inform a large upcoming ($N = 350$) RCT on ImCT in the UK next year. The National Institute for Health Research recommend sample sizes for a feasibility study of 30 in total (15 per arm) or a range of 24 to 50 in total (12 to 25 per arm) (Julious, 2005; Lancaster, Dodd, & Williamson, 2004; Sim & Lewis, 2012). Our study also meets those requirements.

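### Shannon entropy, the only variability index named for the daily mood scores, ignores score size and day order, so it can miss smaller swings or rise as they shrink; add within-person SD and RMSSD by phase.

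*Combined protocol and SAP*

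**What the plan says.** Section 6.1.1 describes the daily rating as a single ordered score: "ranging from -4 (severe depression, admission required due to severe dysfunction) to 0 (stable mood) to +4 (severe mania, admission required due to severe dysfunction". Section 2 counts the daily series as one of two ways in which the primary outcome, mood variability, is measured. Section 4.4 gives its place more exactly: "Next to the ALS-18 as primary measure, we also use daily mood variability scores, using the NIMH-LCM, for the within subjects-design".

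Section 8 sets the purpose of the daily analysis: "to assess reductions in mood variability during the interventions (ImCT, psychoeducation) compared to mood variability during the baseline period". The raw scores become the states of a sequence ("Sequences consist of a series of subsequent states (daily scores"). Optimal Matching distances feed a cluster analysis. Entropy is then introduced as the index of variability, with "Entropy is a measure of diversity of states (a measure of mood variability) within sequences", and is said to be an index that "varies between zero (all sequences in the same state) to 1 (maximum diversity".

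No SD, successive-difference measure or other index that uses score size is specified for each patient's daily scores. Section 8 also says that stretches of the sequence at the start of treatment, during treatment and in follow-up will be compared, but names no statistic. Substitution costs for Optimal Matching are not given.

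**The concern.** A rating of -4 is further from stable mood than a rating of -1, and a change from -4 to +4 is larger than a change from 0 to -1. Entropy sees neither fact. It depends only on the proportion of days in each category, so relabelling the nine scores or shuffling the days leaves it unchanged. This holds even when entropy is calculated for each patient within each phase, so it is separate from the question of which form of entropy is meant.

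The daily series is there to show whether mood variability falls from each patient's own baseline. If entropy is the index that is read, a real reduction in swing size can leave it flat or move it upwards. The study is meant to inform a larger trial of about 350 patients, so the choice of daily index may be carried forward.

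**Working it through.** **Inputs.** Nine states, -4 to +4 (section 6.1.1). Baseline of 28 days; treatment of 84 days for ImCT or 42 for psychoeducation (sections 3 and 8). All mood series below are constructed for illustration; the documents contain no daily data.

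**Formulas.**
- Normalised entropy: H = -Σ p_k ln(p_k) / ln 9, where p_k is the share of days in state k.
- SD: within-series standard deviation (divisor n).
- RMSSD: square root of the mean squared difference between successive days.

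**The plan's own range.** One state only: H = 0. All nine states used equally: H = ln 9 / ln 9 = 1. The stated range of 0 to 1 reproduces.

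**Size and order, 28 days.** Two states used equally give H = ln 2 / ln 9 = 0.693/2.197 = 0.315, whichever two states they are and in whatever order.

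| Series | H | SD | RMSSD |
|---|---|---|---|
| Alternating 0/-1 | 0.315 | 0.50 | 1.00 |
| Alternating -4/+4 | 0.315 | 4.00 | 8.00 |
| 14 days at -4, then 14 at +4 | 0.315 | 4.00 | √(64/27) = 1.54 |

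An eightfold difference in swing size (4.00/0.50) does not register, nor does daily switching against a single switch.

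**Wrong direction, 28 days.** The repeating pattern -1, 0, +1, 0 has shares 1/4, 1/2, 1/4, so H = 1.5 × ln 2 / ln 9 = 0.473, with SD √0.5 = 0.71 and RMSSD 1.00. Moving to it from -4/+4 alternation raises H from 0.315 to 0.473 while the SD falls from 4.00 to 0.71 and RMSSD from 8.00 to 1.00.

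**Where entropy behaves well.**
- One-point-a-day cycling over 28 days: range -4 to +4 gives H 0.987 and SD 2.40; range -1 to +1 gives H 0.473 and SD 0.71. Entropy falls with amplitude. RMSSD is 1.00 for both and does not see the difference.
- Cycling between -2 and +2 in baseline, then constant 0: H goes from 0.709 to 0.
- Simulated 28-day AR(1) series (assumed autocorrelation 0.5 and 0.8, latent SD 0.3 to 2, rounded to the scale): correlation of H with SD about 0.95.

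**Constant low mood and recovery.**
- Constant -3: H = 0, SD = 0, RMSSD = 0.
- Stepwise recovery over the 84 treatment days (21 days each at -3, -2, -1, 0): H = ln 4 / ln 9 = 0.631, SD = √1.25 = 1.118, RMSSD = √(3/83) = 0.19.

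All three indices call the constant patient perfectly stable, and all three rise during the recovery, RMSSD only slightly.

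**The case against.** The strongest reply is that the damaging examples are selected. They rely on jumps between two states. Where mood passes through intermediate scores, larger swings occupy more states and entropy rises with them, as the one-point-a-day and AR(1) results show. Runs at -4 or +4 are also unlikely to persist in this trial: section 6.1.1 ties both ends of the scale to a need for admission, and section 6.4.1 removes patients who relapse and are admitted for more than a week. This stands, and it limits how often the fault would bite. It does not remove it: the size-blindness is a mathematical property, and it applies equally to shifts between, say, -2/+2 and -1/+1.

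A second reply is that section 8 never states entropy as the test of baseline against treatment. Entropy is plotted and, as an exploration, regressed on gender and medication. That also stands. A reader might infer that the plan's daily result will be null or of the wrong sign; the documents do not support this, because no such test is specified. What remains is that the stated purpose is to assess a reduction in variability, and entropy is the only index offered for it.

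A reader might also infer that entropy scores recovery as greater variability. As a general statement this is wrong. Cycling that settles at 0 lowers entropy, and steady low mood that lifts gives 0 in baseline and 0 again in follow-up once mood is constant. That constant depression looks stable is true of any variability index, including SD and RMSSD, and is no special fault of entropy.

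Optimal Matching could take account of score distance through its substitution costs. These are not stated, and the method gives distances and clusters, not a measure of variability.

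**Conclusion.** The point holds in a limited form. Entropy, the only index that section 8 equates with daily mood variability, discards the size and order of the scores. It can therefore miss a reduction in swing size (0.315 for SDs of 0.5 and 4.0 alike) and can rise when swings shrink (0.315 to 0.473 while the SD falls from 4.0 to 0.71). How far this would distort the trial's daily results depends on how patients' scores actually move: little if they vary smoothly, more if they jump between a few states. The documents give no daily data from which to tell.

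The figures rest on constructed series and on entropy normalised to nine states. The ALS-18 between-group analysis, on which the sample size is based, is not touched. Section 8's mixed use of transversal and longitudinal entropy is a separate matter, and settling it would not cure this one. The change is worth making before analysis but does not threaten the main comparison.

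**What to change.** In section 8, for the comparison of baseline with treatment and follow-up, specify for each patient and phase:
- the within-person SD of the daily -4 to +4 score, as the measure of amplitude;
- RMSSD over adjacent recorded days, as the measure of day-to-day instability;
- the phase mean, reported beside them so that a change in level is not read as a change in variability.

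Keep entropy as a descriptive display. If Optimal Matching is kept, set substitution costs proportional to the absolute difference between scores, so that -4 and +4 lie further apart than -4 and -3.

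The cost is analysis-plan wording and a few lines of code, with no new data collection. Neither index is enough alone: SD also picks up a trend within a phase (1.118 in the stepwise recovery), while RMSSD misses amplitude when mood moves one point a day and loses pairs of days where a rating is missing. The two should be read together.
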